17.6.5. Vital Signs

Descriptive statistics for vital signs (eg, systolic and diastolic blood pressure, pulse rate, respiratory rate, temperature, and body weight) and their changes from baseline at each visit and at the end of treatment visit will be presented.

Vital sign values are potentially clinically significant (PCS) if they meet both the observed value criteria and the change from baseline criteria. The criteria for PCS vital sign values will be detailed in the Statistical Analysis Plan (SAP). A listing of all AEs for subjects with PCS vital signs will also be provided.

17.6.6. Clinical Laboratory Parameters

Descriptive statistics for clinical laboratory values in International System of Units (SI units) and changes from baseline will be presented for each clinical laboratory parameter.

The number and percentage of subjects with PCS post-baseline clinical laboratory values will be tabulated. The criteria for PCS laboratory values will be detailed in the SAP. A listing of all AEs for subjects with PCS laboratory values will also be provided.

17.7. Immunogenicity Analyses

Immunogenicity variables include anti-AUX-I/anti-AUX-II binding antibody results. Binding antibody levels will be determined from samples collected on Days 1 and 71 during the treatment phase and Day 360 during the observational phase.

Descriptive statistics (percent of positive measurements and average antibody level) will be presented for anti-AUX-I and anti-AUX-II antibody levels at each time point by region treated and overall. Average antibody levels will be summarized on logarithmically transposed titer values.

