
Efficacy:
 
 • PR-PCSS while viewing digital images of the selected quadrant: 5-point scale ranging from 0 (no cellulite) to 4 (severe cellulite) (approximately every 3 months after initial injection [either an injection in previous study EN3835-201 or after an injection in this study]). If treatment is administered in this study, PR-PCSS will be obtained at Screening B (Baseline), Days 22, 43, and 71 after initial treatment within this study. • Investigator using the CR-PCSS by live assessment: 5-point scale ranging from 0 (no cellulite) to 4 (severe cellulite) (every 3 months after initial injection [either an injection in previous study EN3835-201 or after an injection in this study]). If treatment is administered in this study, CR-PCSS will be obtained at Screening B (Baseline), Days 22, 43, and 71 after initial treatment within this study. • Investigator rating of cellulite severity using the total score from the Hexsel CSS: scores can range from 0 (no cellulite) to 15 (extremely severe cellulite) (Day 360). If treatment is administered in this study, Hexsel CSS will be obtained in this study at Screening B (Baseline) and Day 71 after initial treatment within this study. • I-GAIS: 7-point scale ranging from 3 (very much improved) to -3 (very much worse) (Day 71) • S-GAIS: 7-point scale ranging from 3 (very much improved) to -3 (very much worse) (Day 71) • Subject satisfaction with cellulite treatment assessment: 5-point scale ranging from 2 (very satisfied) to -2 (very dissatisfied) (Day 71)

Safety:
 
Safety will be assessed throughout the study through the recording of:
 
 • Adverse events (AEs) • Vital signs • Clinical laboratory tests • Immunogenicity assessment (ie, assessed through the determination of binding and neutralizing anti-AUX-I and anti-AUX-II antibody levels) 
In addition, for subjects treated with EN3835 in this study, injection site reactions/local tolerability in treated quadrant (through subject and Investigator reporting) will be assessed.

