
Statistical methods:
 
Sample Size Consideration:
 
Approximately 350 subjects are planned to obtain adequate long-term safety data for this study.
 
Analysis Populations:
 
Observational population: The Observational population is defined as all subjects rolled over from study EN3835-201 who do not receive any treatment in the current study.
 
Safety population: The Safety population is defined as all enrolled subjects who received at least 1 injection of EN3835 in this study.
 
Effectiveness population: This population is defined as all safety subjects who have a baseline and at least 1 post-injection evaluation of both the CR-PCSS and PR-PCSS.

Name of Sponsor/Company: Endo Pharmaceuticals Inc.
Name of Investigational Product: EN3835
Name of Active Ingredient: Collagenase clostridium histolyticum
Durability Population: This population is defined as all active responders who have both CR-PCSS and PR-PCSS at 180 days or above. The active responders are subjects treated with EN3835 with improvements of at least 1 level on each scale (CR-PCSS and PR-PCSS) from the baseline.
Efficacy Evaluations: The composite endpoints for cellulite severity assessment, the proportions of composite responders with improvement of 2 (or 1) or better on each scale (CR-PCSS and PR-PCSS), will be summarized as numbers and percentages by study days (visit). The analysis will be based on the Effectiveness population. All other endpoints including observational endpoints will be summarized by study days using appropriate descriptive statistics. The descriptive statistics will include the number and percentage for categorical response variables and number, mean, standard deviation, minimum, and maximum for continuous variables. Durability of treatment effect will be based on the durability populations.
Safety Analysis: The following variables are safety endpoints: 
• AEs: Mapped to preferred term using the Medical Dictionary for Regulatory Activities (MedDRA)• Vital signs• Clinical laboratory tests AEs will be summarized by proportion of subjects reporting each event. Descriptive statistics will be presented for actual and change from baseline at each visit for vital signs and for each clinical laboratory test parameter. Immunogenicity: Anti-AUX-I and anti-AUX-II antibody levels will be summarized using descriptive statistics for the actual value at the visit.

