NOTE: EN3835 is a foreign protein and Investigators must be prepared to address and manage an allergic reaction should it occur. At the time of each injection, a 1:1,000 solution of epinephrine for injection, 50-mg diphenhydramine injection or a suitable equivalent, and oxygen should be available and the Investigator and site staff must be familiar with their use.

Care Procedures After Injection

To evaluate the subject for possible immediate immunological AEs, the subject will remain in direct observation of medical personnel who are skilled in the management of an allergic reaction for 30 minutes after receiving the injection of study drug and until the subject exhibits no sign of an immunological or other clinically significant systemic or local AE. The subject's vital signs should be stable before the subject can leave direct observation (see section 14.8).

The Investigator or qualified designee will then apply a sterile dressing to the injection site with hypoallergenic tape. The subject will be instructed to remove the dressing in the evening.

12.1.4.3. Treatment Session 2 (Treatment Visit 2/Day 22 ± 3 Days) and Treatment Session 3 (Treatment Visit 3/Day 43 ± 3 Days)

Pre-injection

1. Record concomitant medications/procedures (section 12.2)
2. Body weight measurements
3. Vital sign measurements (section 14.8)
4. Collection of samples for urine pregnancy testing (section 14.7)
5. Digital photograph of selected quadrant before dimple marking (section 13.1)

6. Subject assessment of the severity of cellulite using photograph of the selected quadrant via PR-PCSS (section 13.1.1.1). NOTE: Complete the subject (PR-PCSS) assessment before the Investigator (CR-PCSS) assessment and before dimple marking.
7. Investigator will conduct an independent live assessment of the severity of cellulite using the CR-PCSS (section 13.1.1.4). The investigator will conduct the assessment of severity only after the subject has completed her rating of her quadrant and without knowledge of the subject's rating of her quadrant.
8. Selection and marking of dimples to be treated (section 12.1.4)
9. Digital photograph after dimple marking (section 13.1)

Injection

Administration of study drug in the prone position (section 12.1.4.2)

Post-injection

1. Record number of dimples treated and number of injections administered
2. Vital sign measurements (section 14.8)
3. Injection site reactions and local tolerability
4. AEs (section 14)

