14.7.1. Anti-AUX-I and Anti-AUX-II Antibodies

Serum samples will be collected and may be tested for binding and neutralizing anti-AUX-I and anti-AUX-II antibodies at Visit 4 of the observation assessments. Additionally, if a subject consents to treatment in the open-label study, serum samples for antibody testing will be collected before injection at treatment visit 1 and at end of treatment/early termination visit 4 of the open-label treatment period. A subset of subject samples may have neutralizing antibodies tested from Day 1 and Day 71 visits; additional samples may be analyzed if results or clinical signs warrant testing.

The serum samples obtained will be processed, stored and then shipped on dry ice to the designated central clinical laboratory before forwarding to Endo's appointed laboratory for the determination of anti-AUX-I and anti-AUX-II antibodies according to the Laboratory Manual.

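### Antibody results are summarised visit by visit with no within-subject change from the pre-injection Day 1 sample, so percent positive cannot separate carry-over from boosting and the number of women boosted stays unknown

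*Combined protocol and SAP*

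**What the plan says.** All references are to protocol Amendment 4.

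- Section 17.7 opens: "Immunogenicity variables include anti-AUX-I/anti-AUX-II binding antibody results". On timing: "Binding antibody levels will be determined from samples collected on Days 1 and 71 during the treatment phase and Day 360 during the observational phase". On statistics: "Descriptive statistics (percent of positive measurements and average antibody level) will be presented for anti-AUX-I and anti-AUX-II antibody levels at each time point". The display is by region treated and overall, and averages are on the log-titer scale.
- The synopsis, under Immunogenicity: "Anti-AUX-I and anti-AUX-II antibody levels will be summarized using descriptive statistics for the actual value at the visit". The sentence just before it gives laboratory tests and vital signs both the actual value and the change from baseline. Sections 17.6.5 and 17.6.6 do the same.
- Section 14.7.1 and Table 3 have serum drawn before injection at treatment visit 1 and again at Day 71. Table 3 footnote m waives the Day 1 draw for a second course when Screening B or Day 1 of that course falls on Day 71 of the preceding course, in this study or in EN3835-201.
- Section 9.2 makes safety and immunogenicity of re-treating or re-dosing previously treated subjects a secondary objective. Section 10.4 gives immunogenicity after repeat exposure as a reason for the design.
- On neutralizing antibody, the synopsis describes the immunogenicity assessment as "assessed through the determination of binding and neutralizing anti-AUX-I and anti-AUX-II antibody levels". Section 14.7.1 says: "A subset of subject samples may have neutralizing antibodies tested from Day 1 and Day 71 visits".

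**The concern.** For a woman who has already received EN3835, the question behind the secondary objective is what the new course adds to her antibody level. That is a change within one woman, from just before the course to after it. Both samples are scheduled, but the plan reports them as two separate cross-sections.

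Some re-exposed women may be antibody-positive before the first open-label injection. For them, positivity at Day 71 carries no information about the new course: the woman whose titer stayed flat and the woman whose titer rose many-fold are each one positive result. The mean log titer does respond to boosting, but it gives one number for the group. It does not show whether a few women rose steeply or many rose slightly, and it comes without a paired interval. At stake is how informative the report will be on a secondary objective. The primary safety objective is not affected.

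**Working it through.** The plan gives no positivity rate, titer, fold-rise threshold or variance for antibodies, so there is no figure of its own to reproduce. All rates below are assumptions that show what the planned summaries can and cannot distinguish.

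**1. Percent positive.** Let q be the share of re-exposed women positive on open-label Day 1, c the share of the remainder who convert by Day 71, and b the share of already-positive women whose titer is boosted. Assume nobody reverts to negative. Then

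Day 71 positivity = q + (1 − q)c,

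and b does not appear.

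| q (Day 1 positivity) | Day 71, c = 0.9 | Day 71, c = 0.5 |
|---|---|---|
| 50% | 95% | 75% |
| 70% | 97% | 85% |
| 90% | 99% | 95% |
| 95% | 99.5% | 97.5% |

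Each entry is the same for b = 0% and b = 100%. Because Day 1 positivity is also reported, conversion of negative women would be visible, for example 50% to 95% in the first row. Boosting of positive women would not.

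**2. Newly positive women from two visit percentages.** With Day 1 positivity p1 and Day 71 positivity p71, the share newly positive lies between max(0, p71 − p1) and min(p71, 1 − p1).

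- p1 = 90%, p71 = 95%: between 5% and 10%.
- p1 = 80%, p71 = 80%: between 0% and 20%.

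The visit summaries alone do not fix the count; paired data do.

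**3. Mean log titer.** If a fraction f of women rise k-fold and the rest are unchanged, the mean rise is f × log10(k).

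| Pattern | Mean log10 rise | Share with ≥4-fold rise |
|---|---|---|
| Carry-over only | 0 | 0% |
| All rise 2-fold | 1 × 0.301 = 0.30 | 0% |
| A quarter rise 16-fold | 0.25 × 1.204 = 0.30 | 25% |
| Half rise 4-fold | 0.5 × 0.602 = 0.30 | 50% |
| All rise 4-fold | 1 × 0.602 = 0.60 | 100% |

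The mean therefore separates carry-over from a group-level rise. With complete pairs, the difference between visit means equals the mean within-subject change. It does not separate the three patterns at 0.30.

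**4. Precision.** With equal variances at the two visits and within-subject correlation rho, the variance of the mean paired change is (1 − rho) times that of a difference treated as unpaired: 0.7, 0.5 or 0.3 for rho = 0.3, 0.5 or 0.7. This matters only to someone building an interval from the visit summaries, since section 17.7 plans none.

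**5. The overall row.** In an assumed 1:1 mix of women with prior active treatment (60% to 100% positive on Day 1) and prior placebo (0% to 10%), pooled Day 1 positivity runs from 0.5 × 60% + 0.5 × 0% = 30% to 0.5 × 100% + 0.5 × 10% = 55%. Such a row mixes carry-over with naive women, so any added analysis should be split by prior exposure.

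**The case against.** The strongest reply is that the plan is not blind to boosting. Day 1 is itself a reported time point and the average is on log titer, so a group-level boost would appear as a higher mean at Day 71. This stands. A reader might infer that the plan would give much the same result whether or not re-exposure boosts antibodies; that is true of percent positive only.

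Section 17.2 requires safety analyses within cohort, and the synopsis lists immunogenicity under safety. Re-treatment and re-dosing women may therefore be tabulated apart from initial-treatment women. This is a reasonable reading, although 17.7 names only region and overall. It still adds no within-subject change. Section 17.2 would also leave a former placebo subject's second course in the initial-treatment cohort, whereas section 12.1.4 labels that course re-treatment or re-dosing.

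A reader might also infer that neutralizing results are shut out of the analysis. The documents do not support that firmly. Section 17.7 says its variables include binding results, which need not be exhaustive. The synopsis sentence on antibody levels can be read as covering both kinds, and the neutralizing assay is optional and in a subset. What remains is a minor lack of detail.

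Finally, the analysis is descriptive, change could be derived later from the same data, and an SAP might add it. Sections 17.6.5 and 17.6.6 expressly defer criteria to an SAP; 17.7 does not, and no separate SAP text was available to check. Deriving change later is possible, but a fold-rise threshold chosen after the titers are seen carries less weight.

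**Conclusion.** The point holds in this form: antibodies get visit-level percent positive and mean log titer of the actual value, with no pairing to the pre-course sample, while laboratory tests and vital signs get a change from baseline. For percent positive, carry-over and boosting are indistinguishable in women already positive on Day 1. For mean log titer, a group-level rise would show, but the number of women boosted would not, and no paired interval is planned.

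The size cannot be stated as a real rate, because the documents give no seropositivity or titer data. The illustrations rest on assumed Day 1 positivity of 50% to 95%, conversion of 50% or 90%, no reversion to negative, and chosen fold rises. That visit positivity mostly reflects earlier exposure is likewise something a reader might infer but cannot show from the documents. This is an inexpensive improvement to a secondary, descriptive analysis. No dose, schedule or clinical rule is involved.

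**What to change.** Add to section 17.7, or to the SAP text that implements it, per treatment course and by prior-exposure cohort (re-treatment, re-dosing, initial treatment, labelled by course as in section 12.1.4):

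1. Within-subject change in log titer for anti-AUX-I and anti-AUX-II, from pre-injection Day 1 to Day 71 and to the Day 360 sample, as a geometric mean ratio with 95% CI.
2. Number and percentage of subjects, rather than measurements, who go from negative to positive, are positive with a fold rise at or above a stated threshold, or are positive without such a rise. Fix the threshold before results are seen.
3. A definition of the pre-course value. Where footnote m waives the second-course Day 1 draw, use the preceding Day 71 sample, including the EN3835-201 Day 71 sample where that applies. The parent-study result must then be brought into the analysis data, after confirming that the sample was drawn, since this protocol does not give the parent study's sampling schedule.
4. Minor: if neutralizing assays are run in the subset, the number tested and number positive at Day 1 and Day 71.

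The cost is analysis wording, a choice of threshold, a link to parent-study antibody data for some subjects, and one or two tables. Items 1 to 3 use samples and binding assays already planned. Item 4 applies only to assays that are run anyway. No extra blood draw is needed.

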17.8. Pharmacokinetic Analyses

Not applicable.

17.9. Interim Analysis

Not applicable.

17.10. Statistical Software

Statistical analyses will be performed using Version 9.3 (or higher) of SAS® (SAS Institute, Cary, North Carolina).

18. STUDY DRUG MATERIALS AND MANAGEMENT

18.1. Study Drug Identity

EN3835 is formerly known as AA4500; the 2 product names should be considered synonymous. The investigational product vials will be labeled as EN3835. The components of EN3835 are 0.9 mg of collagenase clostridium histolyticum, [REDACTED] in a lyophilized cake.

The components of EN3835 sterile diluent for reconstitution are 0.03% (2mM) calcium chloride (CaCl_2) in 0.9% (154mM) sodium chloride (NaCl) solution, pH 6.0 to 7.0. Diluent is supplied as a terminally-sterilized liquid at 3.0 mL per vial.

18.2. Study Drug Packaging and Labeling

Sterile vials of lyophilized EN3835 and sterile diluent will be provided to the Investigator by Endo. Each kit will contain 2 vials each of EN3835 and sterile diluent.

18.3. Study Drug Storage

All study drug will be provided by Endo. Study drug must be kept in a refrigerator (2°C-8°C) with locked access.

18.4. Study Drug Preparation

Refer to the Reconstitution Instructions for detailed preparation instructions.

Before reconstitution, remove the vials containing the lyophilized study drug powder and the vials containing the sterile diluent from the refrigerator and allow the vials to stand at room temperature for 15 minutes. Designated study personnel will visually inspect the study drug vials to determine the integrity and acceptability of the lyophilized drug product for reconstitution. The written procedures for inspection of the study drug vials will be provided to the site by Endo.

[REDACTED] The reconstituted study drug solution should be administered as soon as possible after reconstitution and further dilution. Each vial of study drug powder for reconstitution will be diluted according to the Reconstitution Instructions. Study personnel will maintain a record of the date and time of reconstitution.

18.5. Study Drug Accountability

Endo or its agent will maintain a master log of kits dispensed to the investigative sites. A drug inventory form must be kept current by the site staff designated to be responsible for reconstitution and must be made available to the clinical monitor, Endo employees, IRB/independent ethics committee (IEC), and regulatory agencies for routine inspection and accountability during monitoring visits. When instructed by Endo, the Investigator agrees to return all original containers of unused study drug to Endo or its designee.

18.5.1. Study Drug Handling and Disposal

The Investigator is responsible for recording the receipt and use of all drug supplied and for ensuring the supervision of the storage and allocation of these supplies. All unused study drug will be returned, and unit counts will be performed whenever medication is returned. The site must account for all study drug received. The Investigator agrees not to supply study drug to any person except to those subjects enrolled in the study. At the end of the study, all unused drug supplies will be returned to Endo as instructed by the clinical monitor.

19. DIRECT ACCESS TO SOURCE DATA/DOCUMENTS

19.1. Source Documents

Source documents include but are not limited to original documents, data and records such as hospital/ medical records (including electronic health records), clinic charts, lab results, subject diaries, data recorded in automated instruments, microfilm or magnetic media, and pharmacy records, etc. At a minimum, all data required to be collected by the protocol should have supporting source documentation for entries in the eCRF.

19.2. Study Monitoring

A representative of Endo Pharmaceuticals Inc. will meet with the Investigator and his/her staff prior to the entrance of the first subject to review study procedures and methods of recording findings in the eCRF.

After enrollment of the first subject, an Endo Pharmaceuticals Inc. representative will be assigned to periodically monitor each Investigator site for study progress and to verify that standards of Good Clinical Practice (GCP) were followed. The Investigator is expected to prepare for the monitor visit, ensuring that all source documents, completed eCRFs, signed consent forms, and other study related documents are readily available for review.

19.3. Audits and Inspections

The Investigator shall permit audits and inspections by the Sponsor, its representatives and members of regulatory agencies. The investigator should immediately notify the Sponsor of an upcoming FDA or other regulatory agency inspection.

19.4. Institutional Review Board (IRB)

The Investigator shall permit members of the IRB/IEC to have direct access to source documents.

